STUDY PROTOCOL

THE EFFICACY AND SAFETY OF FIRST LINE ANTI-EPILEPTIC DRUGS (AEDs) AS SUBSTITUTION THERAPY FOR CHILDREN WITH DRUG RESISTANT EPILEPSY

Protocol Number 22-09-1097

ABSTRACT

Background: Drug resistant epilepsy occurs around 30% of children with epilepsy. It is the failure to get seizure-free after combining two or more anti-epileptic drugs whether first- or second-line ones. Previous studies focus on the efficacy and safety between the two groups whether as add-on or substitution therapy mostly in newly diagnosed epilepsy children. However, the study that investigate first line Anti-epileptic Drugs (AEDs) as substitution therapy compared to second-line ones particularly among drug resistant epilepsy children is still lack. **Design**: It is an open-label, randomized controlled trial, which will be conducted in three referral hospitals in Jakarta, Cipto Mangunkusumo, Harapan Kita, and Fatmawati Hospital, from November 2022 until April 2023. The data will be collected from electronic medical record consisting of demographic, clinical characteristics, and brain CT scan or brain MRI, and diary cards that record daily drug consumption and adverse drug reaction. Self-administered QOLCE-55 questionnaire is used to assess the quality of life of the children. Furthermore, there will be EEG and laboratory examination prior and after intervention. The data will be recorded on Case Report Form that is filled by the researcher. Ethics committee approval is obtained from The Ethics Committee of The Faculty of Medicine, University of Indonesia-Cipto Mangunkusumo Hospital. Research permits would be issued by each institution where the study will take place.

Sample: There will be 100 participants, divided into 2 groups, the intervention and control. Fifty children in the intervention group will be treated with first line AEDs as the substitution therapy, while the other 50 participants in the control group will get second-line AEDs. The sample size is calculated based on the difference proportion of two independent groups.

Duration of the study: The study will take 14 weeks as a whole that consists of 6 phases including baseline, initial, titration, maintenance, tapering-of, stopping and another maintenance phase.

Introduction

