Randomized studies in drug-resistant epilepsy typically involve addition of new anti-epileptic drugs. However, in clinical practice, if the patient is already taking multiple drugs, then substitution of one of the current medications commonly occurs, despite little evidence supporting this approach.²² The choice of the substitution drug depends on the mechanism of action, the pharmacokinetic profile, drug-drug interaction, and the risk of seizure exacerbation as well as patients-related factors. The new combination is intended to maximize efficacy and minimize toxicity. However, the availability and cost-effectiveness should also be

taken into consideration since the patient would not reach the goal of ideal combination of drugs if they could not afford it nor even get the medication. ²³⁻²⁶ Another considerable case is one of drug resistance patterns in which at the first-time patients may not responsive to treatment yet they change into a state that is responsive to the medication. ²⁷ The choice of substitution therapy may originate from firs-line AEDs since evidences have shown they have equal efficacy to those of second-line ones. However, there is still lack of evidence whether the drug resistance pattern occur if the substitution drug is originated from first-line AED even more if it has ever been given prior to the current drug combination. ²⁷ The study aims to analyzed the efficacy and safety of first-line AEDs as substitution therapy in drug-resistant epilepsy children.

Primary Objective

The primary outcome of the research is to analyze the proportion of responders, who are defined as subjects who get 50% of seizure reduction.

Secondary Objectives

There are some secondary objectives of the study. The first one is to analyze the differences of improvement of quality of life, EEG feature and time to achieve seizure reduction, between the intervention and the control group. Besides, the research will describe the clinical characteristics, adverse effects of the drugs and laboratory features related to the adverse effects, among children with drug-resistant epilepsy. Furthermore, it will explain factors influencing the reduction of seizure frequency

Study Design

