including seizure frequency, seizure type, seizure onset, medication history, family history of seizure, and also developmental stages, will be recorded from electronic medical record. Besides, the CT-scan or MRI are also collected from the same source. After that, their quality of life will be assessed by QOLCE-55 validated questionnaire through self-guided report. Furthermore, the laboratory investigation and EEG will be performed.

The next phase is intervention phase, started from initial step and ended by the maintenance of new combination therapy, which takes with overall 12 weeks. Initially, the substitution drugs with each initial dose are consumed. The drugs consist of valproic acid for the generalized and carbamazepine for focal epilepsies. On the other hand, the control group will take lamotrigine or clobazam for generalized and oxcarbazepine for focal ones. The phase continuous to titration dose, in which, the dose is raised gradually until it causes 50% of seizure reduction, and the next step is maintained the dose for about 2 weeks.

The following is tapering-off and after that stopping the substituted drug, levetiracetam or topiramate, which is determined by considering individual condition. Yet, if the seizures increase more than one and a half time of the previous frequency during the phases, the intervention will be ended immediately. On the contrary, if the condition is better, then the children go to the maintenance of new combination, that is the substitution drug and the old drugs in which the seizures do not go up or even better keep going down. The children who complete all of the phases are categorized as responder. In case if the intervention is ended, the subjects will be given the former combination therapy with adjusted doses in order to decrease the seizures until reaching the pre-intervention condition. The subjects are categorized as non-responder, and will be dropped-out. The other criteria of drop-out are resignation, non-compliance of study procedure, and death in term of other causal not related to the study. While in term of lost to follow-up, is intended for those who do not attend the study without any possible reasons.

[figure not shown]

Figure 2. flow-chart of the study

Maintenance the dose of the new combination therapy that consist of the new drug and

Maintenance

old drug after stopping the substituted drug

Inclusion criteria

- 1. Children age at 1 18 years old

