- 2. Children diagnosed as drug-resistant epilepsy by pediatric neurologists, diagnosis was based on the ILAE 2017 criteria
- 3. Children will have got at least 3 months of combination therapy that consists of levetiracetam of topiramate with optimal of therapeutic dosages

Exclusion criteria

- 1. Non-convulsive epilepsy
- 2. Suffered from status epilepticus in the prior 3 months before the study begins
- 3. Past medical history of idiosyncrasies or severe adverse drug reactions caused by the substitution therapy that will be given

Instrument of the study

QOLCE-55 questionnaire

Once the children are enrolled, quality of life will be assessed by using validated QOLCE-55 questionnaire. It is parent-reported and self-administered questionnaire which assess quality of life children with epilepsy age 4-18 years of age. The researcher will give a detail explanation about filling the questionnaire. It has 55 questions including cognitive (22 items), emotional (17 items), social (7 items) and also physical (9 items) function. Items are rated on a five-point Likert scale, 0 = very often, 1 = fairly often, 2 = sometime, 3 = almost never, 5 = never. The composite score is the unweighted average of the four subscales, ranging from 1-100, higher score indicates better quality of life.²⁸

Diary Card

The other important thing to evaluate is subjects' adherence, seizure frequencies, and adverse drug reaction by self-reported diary card which is filled by the parents each day during the intervention phase. Besides, drug consumption compliance is also assessed by counting the tablets or powder packages during routine visits of the study.

Electronic Medical Record

Electronic Medical Record is used to collect secondary data that include demographic data, clinical characteristic, and imaging such as brain-CT or brain-MRI.

Laboratory Examination

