The test is performed in hospitals' laboratory where the study take place and is done twice, at the baseline and post intervention phase. The order of the blood test consists of complete blood test, liver function test including alanine and aspartate transaminase, kidney function test including urea and creatinine, and also blood electrolyte that consist of natrium, kalium and calcium. The laboratory professional takes the blood from vein of the arm. The subjects are seated or lying down, accompanied by the parents, while for the younger children, they seat on his/her parents' lap or position that make them feel comfortable. Older children may be asked to make a fist and then will be tied by a rubber band around his/her arms. After that, the needle is inserted the needle until the blood is drawn. The laboratory worker will take the needle since the amount of blood is enough and puts an adhesive bandage over the site. The next step is analyzes of the sample and the result will be issued for about 1-2 days both printed or provided on the electronic medical record.

Electroencephalography Examination

The EEG examination is operated two times, at the baseline and post intervention phase, with high density machine (Caldwell Easy III) is done twice, pre- and post-intervention. The machine will operate for about 45 minutes including 5 minutes each for eye-open and eye-close in every subjects. Beginning with acquisition, EEG recordings use standard parameter to analyze brain activity at various frequencies to gain good quality and artefact-free result. The printed results of the EEG is available for about 4-7 days after the examination.

Data collection

All relevant data will be recorded, by nominated member(s) of the research team, on a case report form (CRF). Each participant will have a CRF and be assigned a unique identification number.

Baseline data

At entry into the study, the following baseline information will be recorded in the CRF:

- unique patient identification number contact telephone number and/or email address
- date of entry into the study
- eligibility for study entry based on inclusion/exclusion criteria
- age at study entry, in years and months
- gender
- weight and height
- seizure type (eg, generalized tonic clonic, absence, myoclonic and partial)
- the age at diagnosis and duration of epilepsy
- seizure frequency or average number of seizures per month

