- current anticonvulsant(s) with doses and formulation and its side effect (if presents)
- other medications and its side effect (if presents)

- first recognized seizure date
- prior EEG and laboratory which has been performed at the baseline phase
- physical examination

Follow-up data

Follow-up data will be collected during regularly scheduled clinic visits (per 2 weeks). This information will be obtained from the participants' diary card. Important information to be collected at follow-up will include:

- physical examination
- adverse drug reaction of the substitution therapy that happen
- seizure's frequency
- type of seizure
- complaint

Outcome evaluation

- a. The difference in responders was the difference in the percentage of responders in the group that used first line OAE again as substitution therapy and those that used standard therapy. Responders are subjects who experience a decrease frequency of seizure more than or equal to 50% of the initial seizure. Frequency of seizure is the number of seizures that occur within 1 month. In previous studies, it was said that the frequency of seizures was said to have decreased significantly or was said to respond if the seizures were reduced by 50% or more from the initial seizure. ^{19, 29} Based on this, researchers will categorize the frequency of seizures into:
 - Responder: there is a decrease in the frequency of seizures by 50% or more than before
 - Non-responder: namely the frequency of seizures remains or decreases but not up to 50% of the initial seizure frequency or the frequency is more than before

Furthermore, the proportion in the form of the percentage of respondents in the two groups is calculated and differentiated, therefore it is classified into two groups:

- Different : when a significant difference is shown in difference of proportion test of the 2 unpaired groups.
- Not different: when there is no significant difference is shown in difference of proportion test of the 2 unpaired groups.

- b. Differences in quality of life: quality of life assessment using QOLCE-55 instrument. The average of each function (cognitive, emotional, social and physical functions) and the average of the total functions are assessed. This variable is categorized into:
 - Different, if there is a difference in the average quality of life
 - Not different, if there is no difference in the average quality of life
- c. Differences in electroencephalography appearance

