P1 proportion of reduced seizure on the new drug (the proportion of reduced seizure on the standard drug in addition to the minimal difference that is considered significant)= 0.7 + 0.25 = 0.95

Q1
$$1 - P1 = 1 - 0.95 = 0.5$$

P
$$(P1 + P2) / 2 = (0.95 + 0.7) / 2 = 0.825$$

Q
$$1-P = 1-0.825 = 0.175$$

In this study, it was found that the proportion of seizure reduction on standard drugs was 70%.³⁰ Therefore the equation:

$$n1 = n2 = \left(\frac{1,96\sqrt{2(0,825)(0,175)} + 0,84\sqrt{(0,95)(0,5) + (0,7)(0,3)}}{0,25}\right)^2 = 49,56 = 50$$

$$n\ 2\ groups=100$$

Based on the formula above, 100 research subjects are required. An additional of 10% from the total number of subjects are needed as there is a possibility of those dropping out, therefore a total of 110 subjects are needed in this study.

Statistical Analysis

- 1. Analysis of differences in the proportion of responders (primary outcome), differences in EEG appearance (secondary outcome) in pediatric epilepsy patients who are resistant to the combination of second line OAE between those who reused first line OAE as substitution therapy and those who used standard therapy. Data type is categorical. Data is analyzed the Chi-square statistical test, if it does not meet the requirements then an alternative test is performed, known as Fisher's multiple test. The significance level (α) is 5% and the research confidence level is 80%. If p value ≤ α is obtained, this means H0 is rejected, which means that there is a difference seen in seizure frequency between reusing first line OAE as substitution therapy and standard therapy.
- 2. Analysis of differences in the mean quality of life with an unpaired T test if the data distribution is normal or Mann-Whitney if data distribution is not normal
- 3. To assess drug effectiveness, the analysis used was the difference in actual failure between those using first line OAE as substitution therapy and those using standard therapy (primary outcome). Formula:

$$ARR = CER - EER$$

CER: the incidence of increased seizure frequency in the standard therapy group ERR: the incidence of increased seizure frequency in the group in substitution therapy with 1st line OAE The increase in seizure frequency in this study shows therapy

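### The quality-of-life test in Statistical Analysis item 2 makes no stated use of the baseline QOLCE-55 score and has no rule for enrolled children younger than the instrument's stated age range

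*Combined protocol and SAP*

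**What the plan says.** - **Objective.** Under Secondary Objectives, the protocol sets out to "analyze the differences of improvement of quality of life" between the two arms.
- **Outcome.** Outcome evaluation, item b, names the QOLCE-55 and the scores: "The average of each function (cognitive, emotional, social and physical functions) and the average of the total functions are assessed". Its decision category is "Different, if there is a difference in the average quality of life". It mentions neither change nor baseline.
- **Analysis.** Statistical Analysis item 2 is "Analysis of differences in the mean quality of life with an unpaired T test if the data distribution is normal or Mann-Whitney", the latter for non-normal data. It names no time point, change score or covariate.
- **Collection.** The Study procedure section, describing the baseline phase, says "After that, their quality of life will be assessed by QOLCE-55 validated questionnaire through self-guided report". The QOLCE-55 section says "Once the children are enrolled, quality of life will be assessed by using validated QOLCE-55 questionnaire". For other measures the second occasion is written out: the abstract says "there will be EEG and laboratory examination prior and after intervention", and the Laboratory Examination section says the test "is done twice, at the baseline and post intervention phase".
- **Age.** The QOLCE-55 section gives the questionnaire's range as 4 to 18 years. The Inclusion criteria admit children from 1 to 18. The text does not say how children aged 1 to 3 are handled in the quality-of-life analysis.

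**The concern.** The objective asks about improvement, while the outcome definition and the test refer to an average. An analyst working from item 2 alone could compare final scores and ignore the baseline, or compare change scores. Both estimate the treatment effect without bias under randomisation, but they are not equally precise, and neither is as precise as an analysis that adjusts for the baseline score the trial already collects. The trial is open label and the questionnaire is completed by parents, so the analysis is best settled before data are seen.

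The age mismatch is separate. Item 2 has no age limit. Taken literally, it would pool scores from children aged 1 to 3 with the rest, although the protocol's own description of the instrument does not cover them.

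What is at stake is the precision and interpretability of one secondary endpoint.

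**Working it through.** The plan gives no quality-of-life effect size, SD, correlation or power, so there is no figure of its own to reproduce. The calculation below compares the possible analyses.

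**Inputs**
- From the documents: 50 children per arm (abstract and Sample size).
- Significance level: two-sided 5%. The plan states 5% for other analyses; item 2 states none.
- Assumed: true effect 0.5 SD; equal SDs (set to 1) in both arms and at both times; baseline-to-follow-up correlation ρ of 0.3, 0.5, 0.7 or 0.8.

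**Step 1: how far the two readings can differ.** Final-score difference minus change-score difference equals the baseline difference between arms. Its standard error is √(2/50) = 0.20 SD, so its 95% range is ±1.96 × 0.20 = ±0.39 SD, whatever ρ is.

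**Step 2: standard deviation under each analysis.**
- Final score: 1.
- Change score: √(2(1 − ρ)) = 1.18, 1.00, 0.77, 0.63.
- ANCOVA on baseline: √(1 − ρ²) = 0.95, 0.87, 0.71, 0.60.

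Change scores beat final scores only when ρ exceeds 0.5. The ANCOVA figure is below both at every ρ used here.

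**Step 3: power at 50 per arm.** The non-centrality is 0.5 / (SD × √(2/50)), referred to the t distribution.

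| ρ | Final | Change | ANCOVA |
|---|---|---|---|
| 0.3 | 70% | 55% | 74% |
| 0.5 | 70% | 70% | 82% |
| 0.7 | 70% | 89% | 93% |
| 0.8 | 70% | 97% | 98% |

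In sample-size terms, ANCOVA is worth 1/(1 − ρ²) = 1.10, 1.33, 1.96 and 2.78 times the children against final scores. Against change scores it is worth 2/(1 + ρ) = 1.54, 1.33, 1.18 and 1.11 times.

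**Step 4: effect of the age limit.** The share of children under 4 is not given. If ages were uniform over 1 to 18, it would be 3/17 = 17.6%, leaving 50 × (1 − 0.176) ≈ 41 per arm. Repeating step 3 with n = 41:

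| ρ | Final, age 4 or older | ANCOVA, age 4 or older |
|---|---|---|
| 0.3 | 61% | 65% |
| 0.5 | 61% | 73% |
| 0.7 | 61% | 88% |
| 0.8 | 61% | 96% |

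The gain from adjustment persists in the same children. At ρ = 0.3, however, restricted ANCOVA (65%) falls below final scores in all 50 per arm (70%), so the restriction is not a route to more power. For final scores, the smallest difference detectable with 80% power rises from 0.57 to 0.63 SD.

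If the share under 4 were 10 to 40%, about 90 to 60 of the 100 children would remain, and final-score power would be about 66 to 49% (normal approximation).

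**The case against.** The strongest defence is that item 2 should be read with its own objective. Improvement requires an earlier and a later score, and the baseline score is collected. On that reading the unpaired test is on change scores and the baseline enters by subtraction. This largely stands: change is the likelier intent. A reader might infer that the plan discards the baseline score, or that a final-score comparison is just as well supported. The documents do not bear that out. What remains is that neither outcome b nor item 2 states the use, and that change scores are still less precise than ANCOVA, markedly so when ρ is low.

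Three other inferences go too far:
- **That no post-intervention QOLCE-55 is planned.** The readable text gives its timing only at baseline or enrolment, but the Study Design section names a post-intervention phase and the two figures are not shown. Absence cannot be claimed.
- **That the false-positive rate is inflated.** It would be 8.8 to 9.5% if someone saw both the final-score and change-score results and picked one. Nothing in the documents suggests that.
- **That the planned test is invalid.** It is not; randomisation keeps it unbiased.

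It is also fair to say that ANCOVA improves efficiency rather than correcting an error, and that a change-score t-test would serve the objective. That is true, but ANCOVA costs almost nothing extra once both scores exist. The defence does not answer the age mismatch, which rests on two statements in the protocol itself.

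**Conclusion.** The point holds in two parts. First, item 2 makes no stated use of the baseline QOLCE-55 score although the objective is improvement. A baseline-adjusted analysis would raise power at 50 per arm by about 4 to 28 percentage points over final scores (74 − 70 to 98 − 70), and by about 19 down to 1 over change scores (74 − 55 to 98 − 97), as ρ goes from 0.3 to 0.8. Second, without an age rule, item 2 would take in scores from children outside the instrument's stated range.

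The power figures rest on the assumed 0.5 SD effect, equal SDs, the assumed correlations and complete scores in exactly 50 per arm. The 41 per arm rests on uniform ages. The age point needs none of these assumptions. Quality of life is a secondary outcome and the primary result is unaffected, so this is a change that should be made, not one on which the trial's main conclusion depends.

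**What to change.** - Replace item 2 with ANCOVA of the post-intervention QOLCE-55 score on arm and baseline score, reporting the adjusted difference with its 95% CI. Name the total score as the main quality-of-life result and the four subscales as supportive. Keep Mann-Whitney on change scores as a sensitivity analysis.
- Limit the quality-of-life analysis to children aged 4 or older at entry. The ground is the instrument's stated range, not precision.
- Report the number of missing scores by arm, including children whose intervention was ended. Seek their post-intervention score where possible, because Study procedure classes them as dropped out. The rule that counts lost children as failures cannot supply a questionnaire score.
- State the post-intervention QOLCE-55 time point in the text. This is a clarification, since the figures may already show it.
- As a clerical check before scoring, compare the printed item codes (0, 1, 2, 3, 5) and the composite range (1 to 100) with the instrument's source.

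**Cost.** Mostly SAP wording, possibly one added parent questionnaire, and follow-up effort for children whose intervention ended. The real price is the smaller analysis set described above, whose size depends on an age distribution the documents do not give.

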This test will use 2 analyses known as intention to treat analysis and per-protocol analysis. Intention to treat analysis means that all research subjects who have been randomized are included in the analysis according to their initial allocation regardless of whether or not the subject is taking the drug/therapy being tested or a placebo, or whether these subjects died before taking the drug being tested. Subjects who did not

failure.

take medication, lost to follow-up, and who moved to another group, are considered failures of their original group.

Whereas per protocol analysis only includes subjects who complete the research to the end.

- 4. Analysis of the difference in time to achieve a decrease in seizure frequency with the chisquare test or if it does not meet the requirements, an alternative test is performed, namely the Mann-Whitney test
- 5. Analysis of clinical characteristics, side effects of OAE, and laboratory findings of complete blood count (hemoglobin, hematocrit, leukocytes, platelets, and type count), liver function (SGOT and SGPT), kidney function (urea and creatinine), and blood electrolytes (sodium, potassium, calcium, chloride) in pediatric epilepsy patients who are resistant to combination second OAE who re-use first line OAE as substitution therapy and who use standard therapy (secondary outcome). All existing data is processed and presented in a table consisting of mean and standard deviation or median and inter-quartile range, as well as frequency distribution.
- 6. Analyzing factors that affect the decrease in the frequency of late seizures (age, seizure onset, seizure type, family history of seizures, developmental delays, history of OAE, initial seizure frequency, initial EEG, brain structural abnormalities) in pediatric patients with resistant epilepsy combination of second line OAE who re-use first line OAE as substitution therapy (secondary outcome).

Data is categorical. Data is analyzed using Chi-square statistical test, if results do not meet the requirements then an alternative test will be performed, known as Fisher's multivariate test and further analyzed with multivariate test and logistic regression analysis. The significance level (α) is 5% and the research confidence level is 80%. Results will show statistically related if value of $p \le \alpha$ is obtained.

Ethics and dissemination

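### The intention-to-treat failure rate behind the ARR is an undeclared composite, and the per-protocol version drops the children whose treatment was ended because seizures rose

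*Combined protocol and SAP*

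**What the plan says.** Statistical Analysis, item 3, sets ARR = CER − EER and labels the comparison a primary outcome ("those using standard therapy (primary outcome). Formula"). The two rates are given as "CER: the incidence of increased seizure frequency in the standard therapy group" and "ERR: the incidence of increased seizure frequency in the group in substitution therapy with 1st line OAE" (the legend prints ERR where the formula has EER). The section adds "The increase in seizure frequency in this study shows therapy" failure; the last word is displaced in the extracted text. No size of increase, reference period or time window is given.

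Two analyses follow. For intention to treat, every randomised child is "included in the analysis according to their initial allocation regardless of whether or not the subject is taking the drug/therapy being tested". The next sentence says that those who did not "take medication, lost to follow-up, and who moved to another group, are considered failures of their original group". Per-protocol keeps only children who finish the study.

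Study procedure has its own rule: "if the seizures increase more than one and a half time of the previous frequency during the phases, the intervention will be ended immediately". Those children go back to the former combination, are labelled non-responders and are dropped out. Children who complete all phases are labelled responders. Outcome evaluation defines a responder differently, as a child with a reduction of at least 50% in monthly seizure frequency.

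**The concern.** CER and EER are defined by one event, a rise in seizure frequency. In the intention-to-treat analysis a child can count as having that event without a rise, by not taking the drug or by changing group. This also sits badly with the sentence just before it, which says that taking the drug does not affect how a child is analysed. The trial is open-label (Study Design), so refusal and switching can differ by arm for reasons unrelated to seizures. A difference in those behaviours would then be reported as a difference in seizure worsening.

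The per-protocol analysis would normally serve as the check on this. But it leaves out children dropped because their seizures rose, who are the clearest cases of the event being counted. Neither version measures the stated quantity, and the analysis is labelled primary.

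**Working it through.** **Plan's own figure.** There is none to reproduce. The documents give no expected CER, EER or ARR. The sample size of 50 per group is for the responder proportion.

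**Intention to treat.** Let r be the share of an arm with a real increase in seizures, and m the share set to failure by rule (non-takers, movers, lost to follow-up). Assume m is unrelated to r. The reported rate is m + (1 − m) × r. All values of r and m below are assumptions.

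- r = 30% in both arms, m = 10% in one arm only: 0.10 + 0.90 × 0.30 = 0.37 against 0.30. The true ARR is 0 and the reported ARR is 7 points in size.
- r = 20% in both arms, m = 10% in one arm only: 0.10 + 0.90 × 0.20 = 0.28 against 0.20. The reported ARR is 8 points in size.
- r = 20% in both arms, m = 10% in both: 0.28 − 0.28 = 0. Equal shares do no harm when there is no true difference.
- r = 30% in control and 20% in intervention (true ARR 10 points):
  - m = 10% in both: 0.37 − 0.28 = 9 points.
  - m = 10% in control only: 0.37 − 0.20 = 17 points.
  - m = 10% in intervention only: 0.30 − 0.28 = 2 points.

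The sign follows the arm: extra failures by rule in control raise the ARR, and in intervention they lower it.

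**Per-protocol.** Let d be the share of an arm ended for a rise and so dropped. All of them are part of r if the two rules use the same reference frequency. With no other losses, the completers-only rate is (r − d) / (1 − d), which is below r whenever d is above 0 and r is below 1. In the limiting case where every rise led to ending, with r = 30% and 20%, CER = (0.30 − 0.30) / 0.70 = 0 and EER = (0.20 − 0.20) / 0.80 = 0. A true 10-point difference would vanish. How near the trial comes to this limit cannot be known from the documents.

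**Labels side by side.**

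| Child | Study procedure | Item 3 |
|---|---|---|
| Rise above one and a half times | ended; non-responder; dropped out | increase, so failure, but absent from per-protocol |
| Smaller rise, completes all phases | responder | failure |
| Moved group or took no drug, recorded count shows no rise | not addressed as such | failure in intention to treat |

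In addition, children whose intervention is ended are treated with the aim of returning to their pre-intervention state. Because item 3 names no window, a count taken later might show no increase. Whether such a child is a failure even in intention to treat therefore depends on a choice the plan has not made.

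**The case against.** **The intention-to-treat rule is a pre-specified worst-outcome composite.** It is stated openly and paired with a per-protocol analysis. Such composites are legitimate, and adding the extra events to the CER and EER definitions would cure the mismatch of wording. That stands as far as it goes. It would not remove the dependence on arm-specific switching, and the per-protocol analysis offered beside it has its own fault.

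**The outcomes being overridden may not exist.** The diary covers the intervention phase, visits are two-weekly, and data up to withdrawal may be analysed. However, nothing provides for seizure counts after a child stops or switches. This stands: the point applies only where a count was recorded, and for children lost to follow-up the outcome is simply missing.

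**The shifts of 7 and 8 points assume all such children are in one arm.** This also stands. They show sensitivity and are not a forecast.

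**A stronger reading is tempting:** that counting any increase as failure contradicts the rule "if the seizures increase more than one and a half time of the previous frequency during the phases", and that adopting that multiple would sharpen the ARR. The documents do not support it. The multiple is a rule for ending the intervention, set against a previous frequency that is not stated to be the baseline month, and it is never called a definition of failure. If the reference is shared, every rise beyond it is also an increase under item 3.

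Nor is the gain secure. With Poisson monthly counts and no true change, any increase flags 42% to 48% of children at 4 to 60 seizures a month, against 26% down to 1% for the multiple at a single look. With six two-weekly looks, each against half the baseline month, the multiple flags 66% down to 12%. Under the plan's 70% and 95% with reduced seizures, assuming those children halve and the rest double, the ARR is 18 to 25 points for any increase and 15 to 24 for the multiple. The comparison reverses with the assumptions, so nothing here rests on it.

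**Conclusion.** The point holds in this form. The intention-to-treat CER and EER mix seizure increase with non-taking, loss and switching, while the plan defines them by seizure increase alone. The per-protocol CER and EER omit children removed because of that increase. The size cannot be fixed from the documents. Under the assumed rates, 10% set to failure in one arm only moves the ARR by 7 to 8 points. Equal shares leave a null difference at zero and shrink a 10-point one to 9.

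The Study procedure rule and item 3 are unreconciled rather than directly contradictory: they serve different purposes, but they give a completer with a small rise opposite labels. Which multiple, if any, should define failure is not judged here. Because the analysis is labelled primary and the change is modest, it should be made before the data are analysed.

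**What to change.** 1. For the intention-to-treat ARR, analyse by allocation using the observed seizure outcome wherever one was recorded, including for non-takers and movers. Count failure by default only where the outcome is missing.
2. Count children whose intervention was ended for a rise in seizures as failures in both analyses. The per-protocol set then becomes completers plus these children.
3. Report the present all-failures rule as a sensitivity analysis and label it a composite of seizure increase, non-taking, loss and switching.
4. Reconcile Study procedure with item 3, so that one stated rule, reference period and window define failure and no child carries two labels. The choice of multiple is left to the investigators.

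**Cost.** Steps 2 to 4 need revised wording and derived variables. Step 1 needs seizure counts to continue for children who stop or switch, which the documents do not now provide for. The diary cannot supply the reference month: the baseline phase lasts three days and seizure frequency at entry comes from the medical record. The rule must therefore say how the two sources are compared.
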